# 5.4.6. Treatment after Initial Evidence of Radiological Disease Progression

Immunotherapeutic agents such as PF-04518600 and/or utomilumab may produce antitumor effects by potentiating endogenous cancer-specific immune responses. The response patterns seen with such an approach may extend beyond the typical time course of responses seen with cytotoxic agents, and can manifest as a clinical response after an initial increase in tumor burden or even the appearance of new lesions.

If radiologic imaging shows disease progression, tumor assessment should be repeated ≥4 weeks later in order to confirm the progression (See Appendix 6). Assigned study treatments may be continued at the Investigator's discretion while awaiting radiologic confirmation of disease progression.

Patients may receive study treatments while waiting for confirmation of progressive disease (PD) if they are clinically stable as defined by the following criteria:

- Absence of clinical signs and symptoms (including worsening of laboratory values) of disease progression.
- No decline in ECOG performance status.
- Absence of rapid progression of disease by radiographic imaging.
- Absence of progressive tumor at critical anatomical sites (eg, cord compression) requiring urgent alternative medical intervention.

If repeat imaging no longer shows PD but rather CR, PR or SD compared to the initial scan, treatment may be continued/resumed. In determining whether or not the tumor burden has increased or decreased, Investigators should consider all target as well as non-target lesions (refer to the Appendix 6).

If the repeat imaging confirms PD, patients should be considered for discontinuation from both investigational products. However, according to the Investigator's clinical judgment and after discussion between the Investigator and the Sponsor, if a patient with evidence of PD is still experiencing clinical benefit, the patient may be eligible for continued treatment with both investigational products. The Investigator's judgment should be based on the overall benefit-risk assessment and the patient's clinical condition, including performance status, clinical symptoms, adverse events and laboratory data.

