2.1. Study Design

This is a Phase 1, open label, multi center, multiple dose, dose escalation, safety, pharmacokinetic, and pharmacodynamic study of PF 04518600 monotherapy in Part A, and PF 04518600 in combination with utomilumab in Part B. Each part includes a dose escalation phase, and a dose expansion phase. A maximum of approximately 210 patients are expected to be enrolled into the study.

Figure 1. Study Schematic

All patients will complete up to 4 weeks of screening. Following the initial dose(s), treatment with investigational product will continue until either disease progression by immune related response evaluation criteria in solid tumors (irRECIST), patient refusal, or unacceptable toxicity occurs, or end of study, whichever occurs first. Patients will be allowed to stay on study, if the treating physician feels that it is in the patient's best interest in the case of radiological progression, and the absence of clear clinical progression. A follow up visit approximately 4 weeks after the last dose for adverse event (AE) and serious AE (SAE) collection will be conducted. Late immune related adverse events will be evaluated up to 98 days after the first dose(s) of Cycle 1. Because atypical tumor responses after growth of preexisting lesions or appearance of new lesions have been observed with immune checkpoint inhibitors, study B0601002 will assess tumor response based on both response evaluation criteria in solid tumor (RECIST) and Immune related Response Criteria Derived From RECIST v1.1 (irRECIST). Survival data will also be collected.

Part A Monotherapy

Part A1 Monotherapy Dose Escalation

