5.8. Efficacy Endpoints

In this First in Patient study anti-tumor activity is a secondary objective.

RECIST 1.1 objective tumor response criteria are stated below:

Evaluation of target lesions:

Complete Response (CR): Disappearance of all target lesions. Any pathological lymph nodes (whether target or non-target) must have reduction in short axis to <10 mm.

Partial Response (PR): At least a 30% decrease in the sum of diameters of target lesions, taking as reference the baseline sum diameters.

Progressive Disease (PD): At least a 20% increase in the sum of diameters of target lesions, taking as reference the smallest sum on study (this includes the baseline sum if that is the smallest on study). In addition to the relative increase of 20%, the sum

must also demonstrate an absolute increase of at least 5 mm. (Note: the appearance of one or more new lesions is also considered progression).

Stable Disease (SD): Neither sufficient shrinkage to qualify for PR nor sufficient increase to qualify for PD, taking as reference the smallest sum diameters while on study.

Evaluation of non-target lesions:

Complete Response (CR): Disappearance of all non-target lesions and normalisation of tumour marker level. All lymph nodes must be non-pathological in size (<10 mm short axis).

Non-CR/Non-PD: Persistence of one or more non-target lesion(s) and/or maintenance of tumour marker level above the normal limits.

Progressive Disease (PD): Unequivocal progression (see comments below) of existing non-target lesions. (Note: the appearance of one or more new lesions is also considered progression).

Following assessments are to be summarized:

- **Overall Response Rate (ORR)** - ORR is defined as the percentage of patients with best overall response (BOR) of CR or PR relative to the appropriate analysis set.

Category of Best Overall Response:

Best overall response: The **BOR** is the best response recorded from start date until the end of study, disease progression or start of new anti-cancer therapy whichever is earlier. Due to the tumor response is not a primary endpoint, CR or PR assessment based on RECIST 1.1 does not require confirmation.

CR: Complete response is defined (per RECIST 1.1) as disappearance of all target and non-target lesions. Any pathological lymph nodes (whether target or non-target) must have reduction in short axis to <10 mm.

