PR: Partial response is defined (per RECIST 1.1) as at least a 30% decrease in the sum of diameters of target lesions, taking as reference the baseline sum diameters.

SD: At least one objective status of stable or better documented at least 6 (-5 Days) weeks (in consideration of study monitoring schedule) after start date and before progression and the start of new anti-cancer therapy but not qualifying as CR or PR.

PD: Progression documented after start date and not qualifying as CR, PR or SD.

Not Evaluable (NE): All other cases. Note that reasons for NE should be summarized and the following reasons could be used:

- Early death : death prior to 6 weeks after start date
- No post-baseline assessments
- All post-baseline assessments have overall response NE
- New anti-cancer therapy started before first post-baseline assessment
- SD too early (< 6 (-5 days) weeks after start date)

Special and rare cases where BOR is NE due to early SD will be classified as ‘SD too early’.

irRECIST

In addition to the RECIST 1.1, this study is also assessing patients' response using irRECIST criteria.

For irRECIST, with the exception of a complete response assessment, only target and new measurable lesions are taken into account. In contrast to RECIST v1.1, the irRECIST:

Requires confirmation of both progression and response by imaging at least 4 weeks from the date first documented, and

Does not necessarily score the appearance of new lesions as progressive disease if the sum of lesion diameters of target lesions (maximum of 5 target lesions, maximum of 2 per organ) and measurable new lesions does not increase by $\geq 20\%$.

The same method of assessment and the same technique should be used to characterize each identified and reported target lesion(s) at baseline and throughout the study.

irRECIST responses are defined as follows:

- **Overall immune-related complete response (irCR):** Complete disappearance of all lesions (whether measurable or not) and no new lesions. All measurable lymph nodes also must have a reduction in short axis to <10 mm.
- **Overall immune-related partial response (irPR):** Sum of the diameters (longest for non-nodal lesions, shortest for nodal lesions) of target and new measurable lesions decreases $\geq 30\%$.

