The best overall response is the best response recorded from the start of the study treatment until the end of treatment without requirement for confirmation. The patient's best overall response assignment will depend on the findings of both target and non-target disease and will also take into consideration the appearance of new lesions.

Table 3. Scenarios of Assignments of Best Overall Response (irBOR) using irRECIST where Confirmation of Response or Progression is Required

Objective status at:				
Assessment 1	Assessment 2	Assessment 3	Assessment 4	ir Best Overall Response
Death				NE
irCR	irCR	irPD		irCR
irCR	NE	irCR	irPD	irCR
irPR	irCR	irCR	irPD	irCR
irPR	irCR	irPD		irPR
irPR	irPR	irPD		irPR
irPR	irSD or NE	irPR	irPD	irPR ^a
irPR	irPD	irPR		irSD
irPR	irPR	irCR	irPD	irPR
irCR	irPR			irPR
irCR	irPD			irSD
irPR	irPD			irSD
irSD or NE	irCR	irPD		irSD
irSD or NE	irPR	irPD		irSD
irSD	irPD			irSD
irPD	irPD			irPD
irPD	Death			irPD ^b
irPD				NE
No or NE assessment				NE
NE	irPD			NE
NE	No or NE assessment			NE
NE	NE	irPD		NE

a. if irPRs are at least 4 weeks apart. b. Death due to disease progression.

- Duration of Stable Disease - Duration of stable disease is defined from the start of the treatment until the criteria for progression are met, taking as reference the smallest tumor measurements recorded since the treatment started, including the baseline measurements. This endpoint is applicable to the subset of patients who achieved a best overall response of stable disease (SD), those patients whose best overall response is not SD will be excluded from this endpoint analysis. A minimum of 6 weeks (with a - 5 days window, which is essentially a minimum of 37 days) interval of two assessments is required for this endpoint.

- Progression free survival (PFS) – PFS is the time from randomization date to date of first documentation of PD based on RECIST, irRECIST or death due to any cause.

Table 4. PFS Outcome and Event Dates

Situation	Date of Progression/Censoring	Outcome
No adequate baseline assessment	Start date	Censored
PD or death \leq 12 weeks after last adequate tumor assessment	Date of PD or death	Event
No PD but withdraw due to clinical progression	Date of last adequate tumor assessment	Event
PD or death $>$ 12 weeks after the last adequate tumor assessment ^a	Date of last adequate tumor assessment ^a documenting no PD prior to new anti-cancer therapy or missed assessments	Censored
No PD		
New anti-cancer therapy given		

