^a If there are no adequate post-baseline assessments prior to the PD or death, then the time without adequate assessment should be measured from the start date; if the criteria were met the censoring will be on the start date.

Reasons for censoring should be summarized according to the categories in Table 5.

Table 5. PFS Censoring Reasons and Hierarchy

Hierarchy	Condition	Censoring Reason
1	No adequate baseline assessment	No adequate baseline assessment
2	Start of new anti-cancer therapy before event.	Start of new anti-cancer therapy
3	Event more than 12 weeks from last adequate post-baseline tumor assessment/start date	Event after missing assessments ^a
4	No event and [withdrawal of consent date \geq start date OR End of study (EOS) = Subject refused further FU]	Withdrawal of consent
5	No event and lost to follow-up in any disposition page	Lost to follow-up
6	No event and [EOS present OR disposition page for any EPOCH after screening says patient will not continue into any subsequent phase of the study] and no adequate post-baseline tumor assessment	No adequate post-baseline tumor assessment
7	No event and none of the conditions in the prior hierarchy are met	Ongoing without an event

^a more than 12 weeks after last adequate tumor assessment.

- Disease Control (DC) – a patient with a BOR of CR, PR, or SD is defined as having DC. The DC rate is defined as the percentage of patients with DC according to the appropriate analysis set. In addition, a DC rate at week X would be to calculate a PFS Kaplan Meier rate at week X.
- Duration of Response (DoR) – for patients with an objective response, DoR is the time from first documentation of PR or CR to date of first documentation of PD or death due to any cause.

Censoring: Same as censoring for primary definition of progression free survival (PFS) used in the study. Duration of response is only calculated on the subset of patients having CR or PR.

- Time to progression (TTP) - TTP is the time from start date to the date of the first documentation of PD.

In TTP analysis, deaths are censored, either at the time of death or at an earlier visit representing informative censoring (non-random pattern of loss from the study).

Censoring: Same as censoring for the definition of PFS. In addition patients who die without PD will be censored on the date of the last adequate tumor assessment that documented no progression.

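### SAP 5.8 gives two windows for unconfirmed best overall response, and SAP 7.2.2 averages censored response durations and stable-disease durations that have no censoring rule

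*SAP*

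**What the plan says.** **BOR.** SAP 5.8 first defines BOR as the "best response recorded from start date until the end of study, disease progression or start of new anti-cancer therapy whichever is earlier" and adds that RECIST 1.1 responses need no confirmation. Later in 5.8, under the derivation of BOR and irBOR, it is the "best response recorded from the start of the study treatment until the end of treatment without requirement for confirmation". Nothing says which statement governs.

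**DoR.** SAP 5.8: "DoR is the time from first documentation of PR or CR to date of first documentation of PD or death due to any cause". It then adds: "Censoring: Same as censoring for primary definition of progression free survival (PFS) used in the study". SAP 7.2.2 prescribes N, mean, standard deviation, minimum and maximum, plus data listings, and does not say how censored durations enter. It names Kaplan-Meier for PFS. SAP 7.1.4 says in general that time-to-event endpoints are analysed by Kaplan-Meier, without naming any endpoint.

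**Duration of stable disease.** SAP 5.8: "Duration of stable disease is defined from the start of the treatment until the criteria for progression are met". The definition restricts the endpoint to patients whose BOR is stable disease and sets a 37-day minimum. No censoring rule follows. SAP 7.2.2 gives it the same mean-type summary as DoR.

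**The concern.** Objective response, DoR and duration of stable disease are secondary endpoints in every part of the study. SAP 7.2.1 says the aim is a tolerable dose that also shows clinical activity by response rate, so response rate informs the judgement on dose. With two BOR windows, two programmers could produce different RECIST response rates from the same data. A plain mean of censored durations is a stated method, and followed as written it understates how long responses last. For duration of stable disease, the SAP leaves open which patients contribute at all. The endpoint matters in practice: Protocol 1.2.1.4 reports 27 Part A1 patients with stable disease as best response, against 2 confirmed partial responses.

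**Working it through.** **1. Which BOR does the second sentence describe?** It does not name RECIST. But irRECIST requires confirmation of response at least 4 weeks later (SAP 5.8 and its Table 3), so a sentence that waives confirmation fits only RECIST BOR. Read as irBOR, it would contradict the table beneath it.

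**2. Do the two windows differ in practice?** Treatment continues to irRECIST progression (SAP 2.1). Protocol 5.4.6 allows dosing while progression awaits confirmation, and even afterwards: "if a patient with evidence of PD is still experiencing clinical benefit, the patient may be eligible for continued treatment". Protocol 7.4 ties the end of imaging to confirmed progression or new therapy, not to the end of treatment.

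| Situation | Window ending at progression or new therapy | Window ending with treatment |
|---|---|---|
| RECIST PD by lesion growth, treatment continued, later PR on treatment | Not counted | Counted |
| Treatment stopped without PD, PR on a later scan before PD or new therapy | Counted | Not counted |

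The first route is narrow. In Protocol Appendix 5, a new lesion means PD whatever the other lesions do, and irradiated target lesions that have not reappeared or grown make the status indeterminate.

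**3. Which sentence is out of line?** Stable disease must be documented "after start date and before progression and the start of new anti-cancer therapy but not qualifying as CR or PR", and DoR runs from first response to first PD. Both fit the window that stops at progression. Under the other window, a first response after PD would give a negative DoR (PD date minus response date). Size: one patient in 20 is 1/20 = 5 percentage points.

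**4. Mean of a censored DoR.** Let T be the true duration and C the censoring time.

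- Censored values entered as complete: the recorded value is min(T, C), never more than T, so the mean cannot exceed the true mean.
- Censored values dropped: a response is kept only if T ≤ C. With independent censoring, longer responses are less likely to be kept, so the mean again falls.

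Illustration with assumed distributions. T is exponential with mean 1. C is exponential with rate p/(1−p), so a proportion p is censored. Then min(T, C) has rate 1 + p/(1−p) = 1/(1−p) and mean 1−p. Its value is independent of whether T or C came first, so the mean of the uncensored values is also 1−p. For p = 0.2, 0.4 and 0.6 the naive mean is 0.80, 0.60 and 0.40 of the truth, either way.

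With a fixed follow-up c = 22 months after response (also assumed) and true mean m:

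| m (months) | As complete: m(1−e^(−c/m)) | Dropped: (m−(m+c)e^(−c/m))/(1−e^(−c/m)) |
|---|---|---|
| 6 | 5.85 (3% low) | 5.42 (10% low) |
| 12 | 10.08 (16% low) | 7.81 (35% low) |
| 24 | 14.40 (40% low) | 9.34 (61% low) |

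Toy example from Protocol 1.2.1.4, durations 10.3 and 44.1+ weeks. Entered as complete: (10.3 + 44.1)/2 = 27.2 weeks, itself a lower bound because the second response was ongoing. Dropped: 10.3 weeks. The ratio is 27.2/10.3 = 2.6.

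**5. Duration of stable disease.** SAP 5.8 gives censoring rules for PFS, DoR, TTP and OS. For this endpoint it gives a start, an end at progression, the subset and the minimum (6 × 7 − 5 = 37 days). Death, withdrawal, new therapy, missed scans and no progression at cutoff are not covered. SAP Appendix 1.3, meant for further endpoint definitions, is still to be written, and Protocol 9.4 does not mention the endpoint. If a patient with no progression date is treated as missing, SAP 6 and 7.1.1 exclude that value and the mean rests on progressors only. Leaving out patients who are still stable pulls the mean down; leaving out early deaths and withdrawals may push it up.

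**The case against.** The first BOR definition is explicit, and the stable-disease and DoR definitions agree with it, so a careful programmer would probably use it. DoR has a censoring rule, and SAP 7.1.4 offers Kaplan-Meier without exception. Listings are already planned in SAP 7.2.2, and Protocol 9.4 lists dates of first response, progression, death and last tumour assessment, so each DoR can be rebuilt. With 2 partial responses among 52 treated Part A1 patients, Kaplan-Meier medians by cohort would rarely be informative.

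Most of this is fair, and it limits the point. It does not remove it: the second BOR sentence remains in the text, the general line in 7.1.4 does not withdraw the mean that 7.2.2 prescribes, and nothing fills the gap for duration of stable disease.

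A reader might infer more than the documents support:

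- That DoR lacks censoring, or that the SAP has no method for censored data. It has both; 7.2.2 does not connect them.
- That a planned table would show the 2.6-fold contrast. The two patients had different tumours at different doses. SAP 7.1 summarises by initial-dose cohort and Protocol 9.4 by dose and/or tumour type, so neither would pool them.
- That the mean duration of stable disease must be too low. The excluded patients include early deaths and withdrawals as well as those with long control.
- That dose finding or error rates are affected. SAP 7.1 calls the summaries non-inferential, and the MTD rests on DLTs.

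**Conclusion.** The point holds as a matter of clarity and descriptive bias in secondary endpoints, and it should be corrected before database lock.

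- **BOR:** the two windows are incompatible in both directions. The documents do not show that any patient would be reclassified; each one who was would move a 20-patient arm by 5 points.
- **DoR:** the prescribed mean is generally low. That direction needs only independent censoring. The size depends on assumptions outside the documents and runs from 3% to 61% across the settings shown, so no single figure should be quoted as the expected bias.
- **Duration of stable disease:** a censoring rule is missing. That the mean would rest on progressors only is an inference from the missing-data rules, not SAP text. The effect cannot be sized, because the documents give no count of stable-disease patients without documented progression.

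**What to change.** 1. In SAP 5.8, delete the sentence that runs BOR to the end of treatment, or align it with the first definition and say that it applies to RECIST BOR.
2. In SAP 7.2.2, replace mean and standard deviation for DoR and duration of stable disease with Kaplan-Meier estimates and the number censored. Where patients are few, rely on the listings already planned and mark censored durations with a plus sign, as Protocol 1.2.1.4 does.
3. In SAP 5.8, give duration of stable disease a named censoring rule, such as the PFS or TTP rule.

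The cost is SAP wording and standard table shells. No new data are needed. Settling this before database lock also avoids making the choice with outcomes visible in an open-label trial.

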- **Overall immune-related stable disease (irSD):** Sum of the diameters (longest for non-nodal lesions, shortest for nodal lesions) of target and new measurable lesions does not meet criteria for irCR or irPR, (compared to baseline) or immune-related progressive disease (irPD, compared to nadir).

- **Overall immune-related progressive disease (irPD):** Sum of the diameters (longest for non-nodal lesions, shortest for nodal lesions) of target and new measurable lesions increases $\geq 20\%$ (compared to nadir) with a minimum absolute increase of 5 mm, confirmed by a repeat, consecutive observation at least 4 weeks from the date first documented.

New measurable lesions: Incorporated into tumor burden (ie, added to the target lesion measurements). In order to be selected as new measurable lesions (≤ 2 lesions per organ, ≤ 5 lesions total, per timepoint), new lesions must meet criteria as defined for baseline target lesion selection and meet the same minimum size requirements of 10 mm in long diameter and minimum 15 mm in short axis for new measurable lymph nodes. New measurable lesions shall be prioritized according to size, and the largest lesions shall be selected as new measured lesions.

New non-measurable lesions: Do not define progression but preclude irCR.

Table 2. Overall Responses Derived from Changes in Target, Non-target, and New Lesions

Measurable disease	Non-measurable disease		
Target and New Measurable Lesions (Tumor Burden) ^a	Non-Target Lesions	New, non-measurable Lesions	Overall response using irRECIST ^b
Decrease 100%	Absent	Absent	irCR
Decrease 100%	Stable	Any	irPR
Decrease 100%	Unequivocal progression	Any	irPR
Decrease $\geq 30\%$	Absent/stable	Any	irPR
Decrease $\geq 30\%$	Unequivocal progression	Any	irPR
Decrease $< 30\%$ and increase $< 20\%$	Absent/stable	Any	irSD
Decrease $< 30\%$ and increase $< 20\%$	Unequivocal progression	Any	irSD
Increase $\geq 20\%$	Any	Any	irPD

^a Decreases assessed relative to baseline

^b Response (irCR and irPR) and progression (irPD) must be confirmed by a second, consecutive assessment at least 4 weeks apart.

Derivation of BOR and irBOR

Examples of objective status sequences and overall response for a tumor assessment interval of at least 4 weeks and at least as long as the minimum assessment time to qualify as SD are shown in [Table 3](#). This will vary for other assessment schedules.

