Events and censoring rules are summarized in Table 6 similarly to PFS but not including death as an event.

Table 6. TTP Outcome and Event Dates

Situation	Date of Progression/Censoring	Outcome
No adequate baseline assessment	Start date	Censored
PD \leq 12 weeks after last adequate tumor assessment or \leq 12 weeks after start date	Date of PD	Event
No PD/ withdraw due to clinical progression	Date of last adequate tumor assessment	Event
PD $>$ 12 weeks after the last adequate tumor assessment ^a	Date of last adequate tumor assessment ^a documenting no PD prior to new anti-cancer therapy or missed visits.	Censored
No PD		
New anti-cancer therapy given		
Death due to any cause		

^a If there are no adequate post-baseline assessments prior to the PD or death, then the time without adequate assessment should be measured from the start date; if the criteria were met the censoring will be on the start date.

Reasons for censoring should be summarized according to the categories in [Table 7](#).

Table 7. TTP Censoring Reasons and Hierarchy

Hierarchy	Condition	Censoring Reason
1	No adequate baseline assessment	No adequate baseline assessment
2	Start of new anti-cancer therapy before PD.	Start of new anti-cancer therapy
3	Event more than 12 weeks from last adequate post-baseline tumor assessment/start date	Event after missing assessments ^a
4	Death prior to PD	Death due to any cause
4	No PD and [withdrawal of consent date \geq start date OR End of study (EOS) = Subject refused further FU]	Withdrawal of consent
5	No PD and lost to follow-up in any disposition page	Lost to follow-up
6	No PD and EOS present OR disposition page after screening says patient will not continue into any subsequent phase of the study, and no adequate post-baseline tumor assessment	No post-baseline tumor assessment
7	No PD and none of the conditions in the prior hierarchy are met	Ongoing without an event

^a more than *12 weeks* after last adequate tumor assessment.

DC, DoR, DoSD, PFS and TTP will be assessed based on RECIST and irRECIST criteria, respectively.

- Overall Survival (OS);
- Overall Survival Rate at 6 months, 1 year and 2 years.

Overall survival is the time from start date to date of death due to any cause.

Censoring: Patients last known to be alive are censored at date of last contact.

Date of Last Contact

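### SAP Tables 4 and 6 count withdrawal for clinical progression without PD as a PFS/TTP event dated at the last scan, although neither definition includes it

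*SAP*

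**What the plan says.** All of this is in SAP 5.8 unless stated.

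- **PFS definition:** "PFS is the time from randomization date to date of first documentation of PD based on RECIST, irRECIST or death due to any cause".
- **TTP definition:** "TTP is the time from start date to the date of the first documentation of PD".
- **Table 4 (PFS):** the row "No PD but withdraw due to clinical progression" has the outcome Event, dated at the last adequate tumor assessment.
- **Table 6 (TTP):** the row "No PD/ withdraw due to clinical progression" has the same outcome and date.
- **Both tables** also have a plain no-PD row, which is Censored at the last adequate assessment.
- **Footnote a** to both tables gives a start-date fallback. It begins "If there are no adequate post-baseline assessments prior to the PD or death", and what it sets is a censoring date.
- **Table 7, row 6 (TTP censoring reasons)** applies to a patient with no PD who has left the study or will not continue, and who has "no adequate post-baseline tumor assessment".
- **Disease control** uses the same curve: "a DC rate at week X would be to calculate a PFS Kaplan Meier rate at week X".
- **irRECIST (Table 2, footnote b):** "progression (irPD) must be confirmed by a second, consecutive assessment at least 4 weeks apart".

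The Protocol bears on this in four places. Section 7.4 calls for a scan whenever progression is suspected. The end-of-treatment footnotes in the Schedules of Activities require a scan only if the last one is more than 6 weeks old (A1/B1) or 8 weeks old (A2/B2). Appendix 5 tells sites not to record PD on the tumor forms when treatment stops without objective progression, but to give global deterioration of health status as the reason. Section 6.4 lists that same reason.

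**The concern.** A programmer following the definitions and a programmer following the tables would get different results for the same patient. The tables also contain two rows with opposite outcomes for that patient, and no stated order.

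The date is a separate difficulty. The last adequate scan is a natural date for censoring, because it is the last time the patient was known to be free of progression. Using it for a failure places the event at a visit where, under RECIST 1.1, progression was not found. For a patient with only a baseline scan, the failure then falls at time zero or earlier.

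What is at stake is the accuracy of the reported PFS and TTP curves, the PFS rates and the week-X disease control rate.

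**Working it through.** The documents give no expected PFS, event count or share of patients leaving this way, so there is no plan figure to reproduce. The check has two parts: tracing the rules for one patient, then sizing the effect under stated assumptions.

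**1. Outcome for a patient with no PD who withdraws for clinical progression**

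| Rule | PFS | TTP |
|---|---|---|
| Definition | not an event | not an event |
| Clinical-progression row (Tables 4, 6) | Event at last adequate scan | Event at last adequate scan |
| Plain no-PD row (Tables 4, 6) | Censored at last adequate scan | Censored at last adequate scan |
| Table 7 row 6, if baseline-only and off study | – | gives a censoring reason |

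A patient who also dies within 12 weeks of the last scan fits two Event rows of Table 4 with different dates.

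**2. Event time if baseline is the only adequate scan**

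Event time = scan date − time origin. Protocol Appendix 5 allows the baseline scan up to 28 days before treatment, and a note there allows 6 weeks before randomization. Read literally, the event time is between −28 and 0 days, or down to −42 under the note. If time runs from the baseline date (SAP 7.2.2) and that means the scan date, it is 0. Footnote a does not help: it is triggered by PD or death and sets a censoring date. Extended by analogy to the start date, it still gives 0.

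This can happen without breaching the end-of-treatment scan rule. With a baseline scan on day −14, no end-of-treatment scan is due until about day 42 − 14 = 28 (A1/B1) or day 56 − 14 = 42 (A2/B2). It does require that the Protocol 7.4 scan was missed or was not adequate.

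**3. Small Kaplan-Meier example (assumed data, n = 20)**

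Three baseline-only clinical progressors have a scan on day −14 and withdraw on days 21, 28 and 35. Of the other 17, seven have events on day 56.

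- Table 4 as written: 17/20 = 0.85 before time zero, then 0.85 × (1 − 7/17) = 0.50 at day 56.
- Event at withdrawal: 0.95, 0.90 and 0.85 at days 21, 28 and 35, then 0.50 at day 56.
- Censored at start: 1.00, then 1 − 7/17 = 0.588 at day 56.

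Dating changes the early curve. Event versus censored changes the later level, here by 8.8 points.

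**4. Simulation (all shares assumed)**

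Inputs: 400,000 exponential progression times per setting; median 12 or 16 weeks; scans 6-weekly, 6- then 12-weekly after week 24, or 8- then 12-weekly after week 24; 20% of progressors leave for clinical progression; baseline scan 14 days before dosing; end-of-treatment scan added when due. The comparison is 26-week PFS against dating at withdrawal.

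| Leavers with a 7.4 scan in the week before withdrawal | 26-week PFS too low by | Cohort failing at time zero or earlier |
|---|---|---|
| all | at most about 0.15 points | up to 0.6% |
| 80% | 0.2–0.4 points | – |
| half | 0.5–0.8 points | – |
| none | 0.9–1.5 points | 3.1–5.9% |

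Example for A2/B2 with a median of 16 weeks and no 7.4 scan: 33.4% against 34.8%. With no 7.4 scan, 10% leavers give 0.5–0.7 points and 30% give 1.4–2.2.

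Other effects at 20% leavers:

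- Censoring these patients instead raises 26-week PFS by 7.0–8.0 points if no later deaths count. It raises it by 1.9–6.3 points if deaths within 12 weeks of the last scan count (assumed median survival after withdrawal of 4 to 26 weeks).
- With 7.4 followed, using the death row instead of the clinical-progression row raises it by 0.5–1.2 points.
- If every leaver has the 7.4 scan and one further scheduled scan without PD after withdrawal, events are dated 3.1–5.1 weeks late and 26-week PFS is 0.5–0.6 points too high.

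For scale, the standard error of a 35% rate at n = 20 is √(0.35 × 0.65/20) = 0.107, about 11 points.

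**The case against.** The strongest reply is that this is a legitimate choice with little effect. SAP 5.8 says that Table 6 summarizes the event and censoring rules, so the tables can be taken as the operative rule, and counting clinical progression as failure is defensible. SAP 7.1 calls the summaries non-inferential. If sites follow Protocol 7.4, the dating error almost vanishes. For irRECIST, a patient whose last scan showed an unconfirmed irPD can also land in this row, and there the scan date is sensible.

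Most of that stands, and it limits the point to a minor one. It does not remove the mismatch between definitions and tables, or the two rows with opposite outcomes.

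Four stronger readings are tempting, but the documents do not support them:

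- **That Protocol Appendix 5 contradicts the SAP.** It is an instruction for completing forms. The SAP row is itself labelled as having no PD, so the two agree, and Appendix 5 supplies a natural trigger for the row.
- **That event times are negative.** The SAP does not define an adequate assessment, and Table 5 row 3 falls back from a post-baseline scan to the start date. On that reading the event is at zero. Only a literal use of the baseline scan date goes below zero.
- **That Table 5 row 6 would censor the baseline-only patient for PFS under the definition.** That row needs an end-of-study record or a disposition page ruling out any later phase. A patient still in survival follow-up may fall in row 7.
- **That events are also dated too late.** This holds only if withdrawal means stopping treatment and scanning continues afterwards. If it means leaving the study, no later scan exists.

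**Conclusion.** The point holds as a minor one. The tables make an event of something that neither definition includes. Under RECIST 1.1 they date it at a scan that did not show PD, and they give the baseline-only patient a failure at time zero at the latest. For TTP, Table 7 row 6 is keyed on no PD and can conflict directly with Table 6.

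The dating error in 26-week PFS is near zero if the Protocol 7.4 scan is done, and about 0.9 to 1.5 points if it is never done. Whether these patients are events or censored matters more. All these sizes rest on an assumed 20% leaver share and exponential progression; the documents give neither.

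A reader might infer that the PFS results would be materially misleading or that a trial decision is at risk. The documents do not support that: PFS and TTP are secondary and descriptive, and the dating error is well below the sampling error in a 20-patient arm.

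**What to change.** Make the definitions and tables in SAP 5.8 agree.

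1. If clinical progression is kept as an event, add it to the PFS and TTP definitions. Tie it to the recorded reason of global deterioration of health status (Protocol 6.4 and Appendix 5).
2. Give it one date: the recorded date of treatment withdrawal for that reason, not the last scan. For irRECIST, an unconfirmed irPD on the last scan keeps that scan's date.
3. State a row order for Tables 4 and 6 that covers documented PD, or death for PFS, within 12 weeks; new anti-cancer therapy; clinical progression; and plain no PD. Align Table 7 row 6 with it.
4. As a sensitivity analysis, apply the current definitions, censoring these patients at the last adequate post-baseline assessment, or at the start date if there is none. Label this as informative censoring.
5. Use the first-dose date as the time origin throughout, including in place of the baseline date in SAP 7.2.2 and the randomization date in the PFS definition; only Part A2 is randomized.

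The cost is SAP wording and one extra table. There are two downsides. The main analysis brings an open-label investigator judgement into the endpoint. The sensitivity analysis moves PFS upward by more than the dating error it accompanies, so it should be read only beside the main result.
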